2. BACKGROUND AND RATIONALE

2.1 Background on Condition, Disease, or Other Primary Study Focus

Over the last two decades, prescription opioids have grown to become a public health crisis. Today, on average 1 in 5 persons with chronic noncancer pain receive an opioid prescription in the U.S.¹ Yet, despite this record level of prescribing, reports of pain in America have not gone down.^{2,3} The greater availability of prescription opioids has been accompanied by an alarming rise in the negative consequences related to their use. In 2015, there were over 365,000 emergency department visits for misuse and 20,101 prescription overdose deaths, more than have ever been recorded in U.S. history.^{4,5} The costs of prescription opioids are staggering. Aggregate costs for prescription opioid harm are estimated at over \$78.5 billion (in 2013 dollars). One-fourth of the aggregate economic burden is publicly funded (i.e., Medicaid, Medicare, and veterans' programs).^{6,7}

While there have been reductions in opioid prescribing, persons 65 years of age and older who take these medications continue to face particular risks. First, these persons are more likely to have started on long-term opioid therapy in the early 2000s for non-progressive musculoskeletal pain conditions and continue on opioids to this day. These are “legacy patients” with chronic pain who progressively escalated to high opioid doses, often over many years. Now as they age, they face additional and very serious risks resulting from continued use. Age-related changes in drug metabolism, multi-morbidity, and polypharmacy place them at risk of falls and death due to respiratory suppression.

The dominant approach to these risks is to screen for aberrant patient opioid behaviors so that clinicians can pre-empt misuse early through review of contractual opioid agreements or by lowering patient dosages.^{8–11} This approach fails the patient in several ways. First, it frames the clinician's judgment task solely as one of determining if the patient is likely a misuser without examining the reasons for misuse. In older patients, control of physical pain is the most common reason for opioid misuse.¹² Labeling patients as misusers can reduce doctor and patient trust, which can hamper future interactions necessary for future care. Second, it ignores situational and

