psychological factors associated with high-dose opioid use. By focusing on opioid misuse alone, it encourages forced opioid tapering that has been associated with opioid overdose and mental health crisis.¹³ Many persons have mental health, trauma-related or polysubstance use disorders that need to be addressed. Directing clinician attention to these comorbid conditions associated with opioid misuse may promote safer and more effective care.

Making these situational and psychological factors more salient may reframe the problem for the physician and patient in a number of productive ways. First, psychological studies of similarity find that an increase in the measure of common features increases the perception of similarity and decreases the perception of difference.¹⁴ The more features of misuse that the survey assessment requires, the greater the perceived similarity the patient has to a referent person who misuses or abuses drugs. Also, an increase in the measure of the distinctive features decreases similarity and increases difference. The more the physician measures the patient's activity limitation, mental health issues, and reactions to traumatic stress, the less likely physicians might be to view the patient as a wrongdoer and more likely to open up new care pathways (e.g. physical therapy, mental health referrals, and sleep medicine) that may improve their condition. In sum, understanding broadly, a patient's pain experience may help address the reasons why these patients use opioids and may prevent problem use. This is superior to simply identifying persons who misuse medication. For 12 years, our team has redesigned choices in the electronic health record to improve patient care. We recently implemented PainTracker,¹⁵ a patient-reported outcome system that focuses on a broad set of outcomes and causes of pain in a person's life to facilitate better health care. As a supplement to our parent grant (P30AG024968), we follow the explicit directives of NOT-AG-22-005 that task researchers with "Developing...strategies for collection of clinical pain data and for assessing, preventing, and managing pain in later life" (**Aim 1**) and the "elucidation of mechanisms underlying pain experience and its consequences in aging" (**Aim 2**). We will also compare rates of referrals and visits to mental health, physical therapy, and sleep medicine in a randomized trial that assigns older adults using long-term opioids to broader pain assessments.

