5. SAFETY ASSESSMENTS

For patients who were noted to have opioid prescriptions abruptly stopped, emergency room visits or hospitalizations with a diagnosis that could represent a serious complication of untreated pain will be extracted from study site EHRs and reported to the Data and Safety Monitoring Board. Relative rate of ED visits between study conditions will also be evaluated.

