5.1 Specification of Safety Parameters

Data elements from qualifying visits for providers enrolled in the study will be collected from the electronic health record. Aggregate counts of total visits across sites for which the intervention was implemented, for high dose opioid patients, if abrupt changes to dose (> 20% morphine equivalent daily dose) were made. Such cases will be examined closely to determine if unsafe drops in opioids occurred.

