5.3 Adverse Events

Per CDC guideline clarification, adverse events are defined as an abrupt discontinuation of opioids for persons whose most recent prescription exceeds > 49 morphine equivalent daily dose; or as reported to study staff.¹ Emergency department visits will also be evaluated as well as *increases* in prescribing > 20% presumably in response to reports of worsening pain.

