7.3 Outcomes

7.3.1 Primary outcome

The primary outcome is the referral rate to non-opioid related care. This includes: mental health, physical therapy and sleep medicine referrals. We will also measure the rate of new starts on antidepressants.

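### None of the four harms named in section 2.1 (falls, respiratory death, overdose, mental health crisis) is pre-specified in the supplied text as a safety event to be counted by arm

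*Combined protocol and SAP*

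**What the plan says.** Section 2.1 sets out the risks. For older patients who continue on opioids, age-related drug metabolism, multimorbidity and polypharmacy "place them at risk of falls and death due to respiratory suppression". Of an approach that attends to misuse alone, it says that "it encourages forced opioid tapering that has been associated with opioid overdose and mental health crisis".

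Section 5 then defines the diagnosis-based safety extraction. Its population is given first: "For patients who were noted to have opioid prescriptions abruptly stopped". Its events are "emergency room visits or hospitalizations with a diagnosis that could represent a serious complication of untreated pain". No code list accompanies that description. The next sentence adds a comparison between arms: "Relative rate of ED visits between study conditions will also be evaluated".

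The subsections add further measures:

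- Section 5.1 counts visits of high-dose patients "if abrupt changes to dose (> 20% morphine equivalent daily dose) were made", with close examination of such cases.
- Section 5.2 allows chart review by the site principal investigator when needed.
- In section 5.3, "adverse events are defined as an abrupt discontinuation of opioids for persons whose most recent prescription exceeds > 49 morphine equivalent daily dose". It also admits events reported to study staff, and evaluates ED visits and prescribing increases above 20%.
- Section 5.4 sends unanticipated events to the IRB and the DSMB, and refers to a separate, detailed Data and Safety Monitoring Plan.

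**The concern.** The harms that motivate the trial and the events that its safety section selects are described in different terms. Section 2.1 speaks of overdose, crisis, falls and respiratory death. Section 5 speaks of complications of untreated pain after an abrupt stop.

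This matters because the trial expects prescribing to change. The secondary hypothesis in section 7.4 is that morphine equivalent dose will fall among high-dose patients who receive PainTracker. A fall in dose need not be a forced taper, but it is the kind of change to which the background attaches overdose and mental health crisis.

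If one of these harms differed between arms, in either direction, the DSMB reports at 6 and 12 months need not show it, and neither need the final results. An excess could go unrecognised. So could a benefit, which is at least as plausible on the protocol's own reasoning, since section 2.1 links forced tapering to the misuse-only focus that it sees in standard practice.

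**Working it through.** No formula applies, and the plan states no figure to reproduce. The check sets the four named harms against each safety measure in sections 4.1, 4.2.2, 5 to 5.5 and 7.2.

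| Measure | Where | Who or what it covers | How a named harm would appear |
|---|---|---|---|
| Diagnosis-based extraction | 5 | ED visits and hospitalizations, patients abruptly stopped only | Only if judged a possible complication of untreated pain |
| ED visits by condition | 5, 5.3 | No diagnosis restriction stated | Unlabelled, and only if the patient reaches an ED |
| Abrupt dose change above 20% | 5.1 | High-dose patients | Not counted: a prescribing event, though cases are examined |
| Abrupt discontinuation above 49 morphine equivalent daily dose | 5.3 | Patients above that level | Not counted: a prescribing event |
| Prescribing increase above 20% | 5.3 | Prescriptions | Not counted: a prescribing event |
| Events reported to study staff | 5.3 | Whatever is reported | Case by case, not systematic |
| Chart review | 5.2 | Cases raising a concern | Case by case, no count by arm |
| Unanticipated events | 5.4 | Event types not named | Case by case, no count by arm |

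**Result.** Of the four named harms, 0 are defined as an event to be counted and compared by arm.

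Three cases show what this means in practice.

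1. A patient continuing on an unchanged dose falls and is admitted directly. There was no abrupt stop, no ED visit and no prescribing change. Only the three case-by-case routes remain.
2. A patient whose dose was raised is treated in an ED for respiratory depression. The visit adds one to the ED rate, and the increase may be recorded if it exceeds 20%. Nothing labels the visit as respiratory depression.
3. A high-dose patient whose dose is cut by more than 20%, without being stopped, attends an ED in a mental health crisis. The dose change and the ED visit are both recorded. The crisis is identified only if examination of the dose change happens to bring it out.

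**Reach of the consent waiver.** Sections 3.3 and 4.2.1 seek a waiver of consent, section 3.5 delivers the surveys through the patient portal, and no study visit is described. Reports to staff are therefore unlikely to be a dependable source of counts.

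**Feasibility.** Section 4.1 schedules ICD-10 codes in every column from screening through follow-up, and section 4.2.2 repeats them for months 10 to 12. Adverse events are not scheduled in follow-up. Section 5 already plans to extract ED and hospital diagnoses from the site EHR. The raw material for labelled counts is thus largely within the planned data collection.

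**The case against.** The strongest case on the other side has five parts.

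**The safety plan is wider than one extraction.** A reader might infer that safety monitoring looks only for complications of untreated pain. The documents do not support that. ED visits are compared between arms, abrupt dose changes are examined, discontinuations and increases are tracked, and chart review and unanticipated-event reporting are available. This stands. What also stands is that none of these routes gives a count by arm of any named harm.

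**The named harms might qualify anyway.** A reader might infer that an overdose, crisis, fall or respiratory event cannot meet the untreated-pain description. That is not shown. The wording is broad, there is no code list, and section 2.1 says that older patients most often misuse opioids to control physical pain. Some overdoses or crises after an abrupt stop could be included. The objection is sound, but it leaves the selection to judgement, and it does nothing for patients who were not abruptly stopped.

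**The monitoring plan is unseen.** Section 5.4 points to a separate document that may list these events. This stands, and it rules out saying that the harms are never counted.

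**These are background risks, not effects of a survey.** Section 2.1 ties falls and respiratory death to continued opioid use, which is present in both arms. Section 3.3 describes PainTracker as adding no risk. A reader might also link "We will also measure the rate of new starts on antidepressants" in section 7.3.1 to polypharmacy and hence to falls, but no passage says that such starts would be net additions to treatment or would cause falls. It is fair that the documents do not show that PainTracker raises any of these risks. The point here is only that the plan would not display a difference if there were one.

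**No safety claim is planned.** The study title speaks of safer use, but the primary outcome is referral and the secondary hypothesis concerns dose. That limits the seriousness of the gap. The DSMB, however, is asked to judge safety whatever claim is made for efficacy.

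**Conclusion.** The point holds as a gap in pre-specification. The supplied text names four harms as risks in this population and plans a labelled count by arm for none of them. The one extraction that uses diagnoses is tied to a different, undefined concept and confined to patients abruptly stopped.

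No numerical size can be attached. A reader might try to work out how far a doubling of these harms would be diluted in the ED-visit rate. That needs the share of ED visits due to each harm, which the documents do not give, so any figure would only restate the assumed share.

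The conclusion rests on two conditions: that the ED comparison is what it appears to be, a rate without regard to diagnosis, and that the unsupplied Data and Safety Monitoring Plan does not already specify these events. If it does, what remains is to bring section 5 into line with it. The change does not affect the primary analysis. It is a modest, inexpensive improvement that is worth making.

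**What to change.** In sections 5 and 5.3, keep every existing measure and add fixed ICD-10 groups, applied to ED visits and hospitalizations of all study patients in both arms, whether or not opioids were abruptly stopped:

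- opioid or sedative overdose and respiratory depression;
- mental health crisis, including self-harm;
- falls and fractures;
- withdrawal or uncontrolled pain.

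Add death from any cause as recorded in the EHR. Put the code list in an appendix, fixed before outcome data are examined by arm. Report counts by arm to the DSMB in its scheduled reports and in the final results, beside ED visits from all causes. Align the list with the Data and Safety Monitoring Plan and cite that plan's event definitions where they already exist.

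The cost is a code list, some extra extraction and a few table rows. The counts will be small and should be presented as descriptive, without tests. They will also be limited to what the site EHR records, so events treated elsewhere and deaths outside the system may be missed. No treatment rule, sample size or primary analysis changes.

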5.1 Specification of Safety Parameters

Data elements from qualifying visits for providers enrolled in the study will be collected from the electronic health record. Aggregate counts of total visits across sites for which the intervention was implemented, for high dose opioid patients, if abrupt changes to dose (> 20% morphine equivalent daily dose) were made. Such cases will be examined closely to determine if unsafe drops in opioids occurred.

5.2 Methods and Timing for Assessing, Recording, and Analyzing Safety Parameters

The Roybal Standing Data and Safety Monitoring Board will be providing oversight for this study, and has determined the cadence of our reporting (6 and 12 months). The data analyst at Northwestern University will pull the required patient data for analysis from the NU electronic health records one month prior to the 6 and 12 month report due dates. The PIs and Co-Is will review in our team

meeting before delivering to the Data and Safety Monitoring Board. When necessary, our NU Site PI ([name]) will conduct chart reviews to investigate any safety concerns.

5.3 Adverse Events

Per CDC guideline clarification, adverse events are defined as an abrupt discontinuation of opioids for persons whose most recent prescription exceeds > 49 morphine equivalent daily dose; or as reported to study staff.¹ Emergency department visits will also be evaluated as well as *increases* in prescribing > 20% presumably in response to reports of worsening pain.

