4.2.2 Enrollment, Baseline, and/or Randomization

Enrollment

This study involves a randomized trial with 286 clinicians to inform the best approaches to patient assessments for opioid at clinical visits. Long-term opioid recipients complete the Current Opioid Misuse Measure as standard clinical practice. PainTracker will appear as part of these required assessments randomly for half the patients of clinicians randomized to the intervention (COMM+PainTracker). If a waiver is granted, enrollment date (RCT implementation date) will be recorded for each clinic.

Assessments

Baseline: At baseline, we will assess clinician baseline prescribing monthly morphine milligram equivalents (MMEs), ICD-10 codes, and ordering data.

Enrollment and Randomization (Day 1). Demographics, inclusion/exclusion criteria, ICD-10 codes, and ordering data.

Intervention start (Month 1). ICD-10 codes, and ordering data, Pain Tracker/COMM completion rates, Referral rates to non-opioid care, adverse events

Continuously measured or monitored. ICD-10 codes, and ordering data, Pain Tracker/COMM completion rates, Clinician

monthly MMEs, Referral rates to non-opioid care, adverse events

Intervention end (Month 9): ICD-10 codes, and ordering data, Pain Tracker/COMM completion rates, Referral rates to non-opioid care, adverse events

Follow-up (Month 10-12): ICD-10 codes, ordering data, Clinician MMEs, Referral rates to non-opioid care.

Randomization

We will use cluster randomization at the physician level to avoid contamination that might occur if individual providers are randomized to multiple interventions. We will carry out block randomization of physicians with respect to historical referral rate (high vs. low) by using a random permutation of physician lists in the statistical computing language R. Patients of clinicians in the first half of the permuted list will receive the PainTracker survey intervention in addition to COMM. The second half will receive the control condition (COMM standard clinical practice). The same intervention (PainTracker survey) will be implemented throughout the 9 month study period. No intervention will occur during the 3 month follow-up period; it will be for outcomes assessment only.

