5.5 Safety Monitoring

This study will leverage the standing Roybal Data and Safety Monitoring Board (DSMB) established by NIH. Reports of our safety measures will be delivered to our Data and Safety Monitoring Board at 6 and 12 months.

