7.3.2 Secondary outcomes

Secondary outcomes include: 1) clinician aggregate monthly milligram (mg) morphine equivalent (ME) and 2) benzodiazepine prescribing. We will estimate the daily milligram morphine equivalent for each clinician by summing the total number of daily morphine equivalents written within a monthly observation period divided by the number of 30 days. For example, suppose a clinician has three qualifying visits over three days in one month and prescribed as follows: Patient #1 is prescribed 200mg ME/day x 30 days, Patient #2 has tapered from 200 mg ME/day to now 100mg ME/day x 30 days and Patient # 3 is on a tapering plan from 60 to 30 mg ME/day and receives 50 mg ME/day x 15 days. The clinician's outcome for that month then equals:

$$\begin{aligned} & [(200 \text{ mg/day} \times 30 \text{ days}) + 100 \text{ mg/day} \times 30 \text{ days}) + (50 \text{ mg/day} \times 15 \text{ days})] \times [1 \text{ Month}/30 \text{ days}] \\ & = (300 \text{ mg} \times 1 + 100 \text{ mg} \times 1 + 50 \text{ mg} \times (\frac{1}{2})) = 425 \text{ mg MED}/[\text{Month}]. \end{aligned}$$

Oral buprenorphine will be excluded from the calculations as it relates to opioid use disorder treatment. Morphine equivalent dose will be computed by standard means described elsewhere.²⁸ Benzodiazepines will be handled similarly to monthly milligram morphine equivalents but with valium morphine equivalents. Qualifying pain visits will be captured by including all ICD-10 pain diagnostic codes and excluding active cancer diagnoses.

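### The dose criterion in section 5.3 tests only the most recent prescription, so read literally it does not flag abrupt stops from concurrent opioids totalling more than 49 MED when the newest is 49 or less

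*Combined protocol and SAP*

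**What the plan says.** Section 5.3 gives the dose-based rule: "adverse events are defined as an abrupt discontinuation of opioids for persons whose most recent prescription exceeds > 49 morphine equivalent daily dose". The same sentence adds a second route with no dose threshold, namely events that reach study staff by report. Section 5.3 also says that emergency department (ED) visits and dose increases above 20% will be evaluated.

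Three other places bear on abrupt stops:

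- Section 5 begins "For patients who were noted to have opioid prescriptions abruptly stopped, emergency room visits or hospitalizations" and sends those with a diagnosis suggesting a serious complication of untreated pain to the DSMB. No dose threshold applies.
- Section 5.1 states "Data elements from qualifying visits for providers enrolled in the study will be collected from the electronic health record" and looks, "for high dose opioid patients, if abrupt changes to dose (> 20% morphine equivalent daily dose) were made", with such cases then examined closely. It does not define high dose.
- Section 5.2 states "The data analyst at Northwestern University will pull the required patient data for analysis from the NU electronic health records", and section 5.5 adds "Reports of our safety measures will be delivered to our Data and Safety Monitoring Board at 6 and 12 months".

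The only rule for adding doses is in section 7.3.2. It serves a secondary outcome and works "for each clinician by summing the total number of daily morphine equivalents written within a monthly observation period", so it does not sum per patient.

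**The concern.** Abrupt discontinuation is the harm that section 5.3 names, and section 2.1 itself links forced tapering to overdose and mental health crisis. A person on long-term opioids may hold two prescriptions at once, for instance a long-acting and a short-acting product. The dose from which such a patient is stopped is the sum of the two, yet the rule reads only the one written last.

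An analyst has to turn this sentence into a query for two DSMB reports. If the query follows the words, some patients stopped from a total above 49 MED drop out of the dose-based count, and the order in which two prescriptions were written can decide whether the same stop is counted. No interim look at efficacy is planned (section 7.2), so these safety reports are what the board works from when it advises on continuation. What is at stake is the completeness of that count.

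**Working it through.** **Inputs.** The threshold (above 49 MED) and the unit tested (the most recent prescription) come from section 5.3. Nothing from section 5 to section 5.5 sums doses per patient. The plan gives no figure on this point, so there is none to reproduce. The regimens below are assumed.

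**Step 1: two rules.**

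- Literal rule: flag if newest > 49.
- Total rule: flag if newest + other concurrent > 49.

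| Older | Newest | Total | Literal | Total rule |
|---|---|---|---|---|
| 60 | 20 | 80 | no | yes |
| 20 | 60 | 80 | yes | yes |
| 45 | 30 | 75 | no | yes |
| 30 | 45 | 75 | no | yes |
| 49 | 49 | 98 | no | yes |
| 90 | 10 | 100 | no | yes |
| none | 50 | 50 | yes | yes |
| none | 49 | 49 | no | no |
| 20 | 20 | 40 | no | no |

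The rules agree for a single prescription. They part only when concurrent prescriptions total more than 49 and the newest is 49 or less. Two prescriptions of 49 or less are never flagged by the literal rule, up to a total of 49 + 49 = 98.

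**Step 2: dependence on writing order.** The first two rows have the same total and opposite results. For illustration, assume that a 60 and a 20 are each written every 30 days, the 20 being written d days after the 60. The 20 is then the newest on (30 − d)/30 of days:

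- d = 5: 25/30 = 83%
- d = 15: 15/30 = 50%
- d = 25: 5/30 = 17%

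These are shares of days under assumed dates, not rates of missed events. At d = 0 both are equally recent, and the text does not say which to use.

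**Step 3: what the other routes catch.**

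- *Report to study staff:* counts the stop at any dose, but only if somebody reports it. Consent is waived, and section 8.1 limits data to medical and billing records and survey completion rates.
- *Section 5:* collects ED visits and hospitalizations after a noted stop. A stop followed by neither is not counted there.
- *Section 5.1:* a complete stop is a 100% change and so exceeds 20%. It is covered if the patient is high dose, which is undefined, and if it shows in data from qualifying visits. A stop by non-renewal, with no such visit, may not show.

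Each route narrows the gap. None ensures that the stop is counted.

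**Step 4: which date the total should use.** Take a 60 written on day 0 for 30 days and a different opioid at 20 written on day 15 for 30 days, neither renewed. Measured on day 40, just before the last supply ends, the total is 20 and the stop is missed. Measured on day 15, when the newest was written, it is 60 + 20 = 80 and the stop is flagged. The date the newest prescription was written is therefore the better reference, and it must be the only one used. If instead the 20 is a new order for the same opioid and formulation, it replaces the 60, the total is 20, and the reduction is not flagged.

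**The case against.** The strongest reply is that this is a point of wording. Section 5.3 tests a daily dose for persons, and the worked example in section 7.3.2 gives each patient a single daily figure, so the most recent prescription may simply mean the current regimen. Section 5.4 also refers to a separate, detailed Data and Safety Monitoring Plan, which is not among the documents and may contain the operational rule. Meanwhile the report route, sections 5 and 5.1, and the team and chart review in section 5.2 all catch some of these patients.

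Much of this stands. A total-dose reading is possible, the coverage elsewhere is real, and nothing shows how often the gap would matter. But the total-dose reading is nowhere stated, the wording points the other way, and a plan that cannot be seen cannot be assumed to settle it. If the sponsor does mean total dose, the edit only records that.

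A reader might infer more than the documents support:

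- *That the trial's safety monitoring misses these stops altogether.* It does not, because the second limb of the definition has no dose threshold and sections 5 and 5.1 give partial cover.
- *That the count is biased between arms.* Nothing in the documents suggests that concurrent prescribing or its order would differ by arm.
- *That stops after a taper to 49 or less are wrongly left out.* A threshold applied at the time of stopping may be intended, so they form no part of this point.

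**Conclusion.** The point holds for the dose-based criterion in section 5.3. Followed as written, that criterion does not flag abrupt stops from concurrent totals above 49 MED when the newest prescription is 49 or less, and its result can turn on writing order.

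The size in patients cannot be given, because the documents do not say how many hold concurrent prescriptions. The conclusion assumes that an analyst applies the sentence order by order and that the separate monitoring plan does not override it. The primary and secondary analyses are unaffected. The text should be changed because a better rule is available at little cost, with moderate confidence that the literal reading would be the one applied.

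**What to change.** In section 5.3, replace the clause on the most recent prescription with: *whose total daily morphine equivalent dose, summed over all opioid prescriptions whose days' supply covers the date the most recent one was written, exceeds 49*. Use that one reference date in both the text and the query. Treat a new order for the same opioid and formulation as replacing the earlier one, not adding to it. Keep the route through reports to study staff.

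The data should already be to hand. Section 4.2.2 lists "Continuously measured or monitored. ICD-10 codes, and ordering data", and the calculation in section 7.3.2 already needs dose per day and days supplied. The query must link orders by patient, not by clinician.

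The cost is one clause, one query and somewhat more events to review. Some cross-tapers and dose reductions will be flagged falsely, because a new product written while the old supply still runs looks concurrent. The team review and chart review already planned in section 5.2 can resolve these. The replacement rule may also undercount a patient whose single drug is split over two orders, which is worth noting in the query specification.
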